	Chemistry	X		X		May be drawn up to 3 days before the day of dosing. Additional assessments may be obtained at the discretion of the investigator.
	Pregnancy test	X		X		Applies only to women of childbearing potential. Where required by local law/ regulation or institutional guidelines, perform once every 28 days (± 7 days). Either a urine or serum test is acceptable.
	CA-125	X		X		May be drawn up to 3 days before the day of dosing
	PK sampling	X		X		Sparse PK sampling will be conducted over multiple cycles of therapy (see Appendix 4 for additional details).
	Stored blood sample for pharmacogenetics	X				Collect once. Sample can be collected at any time if not collected on Day 1 of Cycle 1.
	Plasma biomarker sample	X		X		Collect only in Cycles 1 and 4. May be drawn up to 3 days before the day of dosing.
	ECG	X	X	X	X	Single local ECG collected at each time point only. Cycle 1 Day 1 and Cycle 2 Day 1: predose, within 15 min after EOI. Cycle 1 Day 15, Cycle 2 Day 15, and Cycle 3-n: Day 1 and 15 prior to each dose. Additional ECGs may be obtained at the discretion of the investigator. When ECGs and PK are required at the same time point, the ECG should be obtained prior to the PK draw.
	Optional tumor biopsy			X		Can occur at any time during patient's treatment. Patients should have adequate neutrophils and platelets prior to biopsy. See Section 9.8.1.

On-Study-Treatment Schedule of Activities

Study Period		Cycle					
		1		2-n			
Cycle/Visit		1		2-n			
Duration		28 days		28 days			
Relative Day within Dosing Cycle		1	15	1	15		
Procedure Category	Procedure					Notes	
Tumor Assessment	Radiologic imaging according to RECIST version 1.1 and tumor measurement (palpable or visible)		X				Perform approximately every 8 weeks (±1 week) up to 1 year, thereafter every 12 weeks (±1 week). The first scan should be approximately 8 weeks (±1 week) from Cycle 1 Day 1. The 8-week/12-week scanning interval should be maintained even if cycles are delayed. As a result, the scans may not always occur at the end of a cycle. The same method of imaging used at baseline should be used for each subsequent assessment. Scans should also be obtained as clinically indicated. Scans to confirm responses may be performed sooner than 8 weeks, but should be at least 4 weeks following the initial observation of an objective response. The next scan should be 8 weeks (±1 week) following the confirmatory scan.

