10.3. Statistical Analyses

Statistical analysis of this study will be the responsibility of Lilly or its designee.

The primary analysis will be conducted approximately 6 months after the last responder's first response date or approximately 1 year after the last patient has been enrolled, whichever occurs first. Additional updated analyses of efficacy and safety may be conducted at later times (approximately 6-12 months after the primary analysis) if deemed appropriate by the sponsor.

All CIs will be given at a 2-sided 95% level, unless otherwise stated.

Any change to the data analysis methods described in the protocol will require an amendment only if it changes a principal feature of the protocol. Any other change to the data analysis

methods described in the protocol, and the justification for making the change, will be described in the statistical analysis plan (SAP) and the clinical study report. Additional exploratory analyses of the data will be conducted as deemed appropriate.

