10.3.1. Efficacy Analyses

Overall response rate (ORR) is defined as the number of patients who achieve a best overall response of complete response (CR) or partial response (PR) divided by the total number of enrolled patients per cohort. The ORR, with corresponding 95% exact CI, will be summarized for each cohort. The posterior estimates of ORR and posterior probability of ORR that is greater than the cutoff value will also be derived via a Bayesian model. See details in Section 10.3.4.

Disease control rate (DCR) is defined as the number of patients who achieve a best overall response of CR, PR or stable disease for ≥ 4 months divided by the total number of enrolled patients per cohort. The DCR, with corresponding 95% exact CI, will be summarized for each cohort.

CA-125 response is defined as $\geq 50\%$ reduction in CA-125 levels from a pretreatment sample. The response must be confirmed and maintained for ≥ 28 days according to GCIG criteria. Patients must have a pretreatment sample that is ≥ 2 times the upper limit of the reference range and obtained within 2 weeks before starting the treatment. The response rate based on CA-125 will be summarized for each cohort.

Progression-free survival (PFS) is defined as the time from the first dose until the first occurrence of documented disease progression per RECIST 1.1, or death from any cause in the absence of progressive disease. Patients known to be alive and without disease progression will be censored at the time of the last adequate tumor assessment (a detailed PFS event/censoring scheme is provided in SAP).

Duration of response (DoR) is defined as the time from the date measurement criteria for CR or PR (whichever is first recorded) are first met until the first date that disease is recurrent or objective progression is observed, per RECIST 1.1, or the date of death from any cause in the absence of objectively determined disease progression or recurrence. The DoR will be censored according to the same rules as PFS.

Overall survival (OS) is defined as the time from the first dose until death from any cause. If the patient is alive, lost to follow-up or withdrawn from study at the time of data analysis, OS data will be censored on the last date the patient is known to be alive.

For time-to-event variables, such as PFS, DoR and OS, the Kaplan-Meier method (Kaplan and Meier 1958) will be used to estimate the curves, median time and 95% CI for each cohort.

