10.3.4. Interim Analyses

Interim analyses will be conducted regularly to evaluate closing enrollment early due to futility. For each cohort, the first futility interim analysis will be conducted after approximately 20 patients have been treated and completed ≥ 2 cycles or have discontinued before the first post-baseline tumor assessment. Although confirmation of response is not required to complete the interim analysis, the interim analysis may be potentially delayed to obtain confirmation of response. The futility rule is based on the posterior probability of activity via a Bayesian model. A cohort will be closed if the posterior probability is less than the prespecified futility threshold (e.g., 20% probability that ORR exceeds the prespecified threshold of activity). Borrowing of information across cohorts may be allowed, and the strength of borrowing may depend on the similarity among the cohorts. The prior distribution of response rate used in the model may be derived from the ongoing NCI-sponsored Phase 2 Study E001 (NCT02203513). The futility rules for each cohort are described as follows (ORR of 25% and 15% are considered the threshold of activity for Cohorts 1 – 3 and 4, respectively):

- Cohorts 1 to 3 (platinum-resistant): $\Pr(\text{ORR} > 25\%) < 20\%$
- Cohort 4 (platinum-refractory): $\Pr(\text{ORR} > 15\%) < 20\%$.

It is planned that enrollment can continue while interim analyses are conducted, but the sponsor may decide to pause the enrollment, if necessary. For the cohorts that can continue after the evaluation of the approximately first 20 patients, subsequent interim analyses will occur after approximately every 20 additional patients. The interval between interim analyses may be adjusted if deemed appropriate based on enrollment rates and available data. At each subsequent interim for each cohort, the posterior probability of response rate will be updated based on the available data and a higher futility threshold for the posterior probability may be adopted if deemed appropriate by the sponsor.

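### Protocol 10.3's earlier-of-two-dates trigger has no minimum follow-up: with few responses or slow accrual it can understate DCR and leave PFS immature, and it understates ORR only if the last responder is judged in real time

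*Protocol*

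**What the plan says.** Protocol 10.3 gives the timing in one sentence. Its first limb runs for about half a year from the date on which the final responder first responded. The second limb, and the rule that joins the two, read: "first response date or approximately 1 year after the last patient has been enrolled, whichever occurs first". It asks for no minimum follow-up, scan or completed best-response assessment. It does not say whether the trigger works study-wide or cohort by cohort, or how the last responder is identified while patients can still respond.

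Three other provisions matter:

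- Table JTJN.2 (on-study schedule): "The first scan should be approximately 8 weeks (±1 week) from Cycle 1 Day 1", with later scans about every 8 weeks in the first year.
- Protocol 10.3.1: ORR is responders "divided by the total number of enrolled patients per cohort". DCR has the same denominator and counts "best overall response of CR, PR or stable disease for ≥ 4 months".
- SAP 5.1 (version 1, April 2018) waits until all enrolled patients have at least 2 months of follow-up and/or completed best-response assessments. The protocol amendment approved in September 2018 removed that condition. Appendix 7 attributes the new timing to an FDA recommendation.

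**The concern.** The first limb depends only on when the last response occurred. If patients enrolled late do not respond, or have not yet responded, it keeps running from an old response and can fall before their first scan. The 1-year limb would protect them, but the earlier-of rule switches it off in exactly that case.

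Patients without enough follow-up stay in the all-enrolled denominators. A patient with ongoing stable disease of less than 4 months counts against DCR. For PFS, SAP Table JTJN.6.1 censors a patient with no adequate post-baseline scan, no progression and no death at or near time zero. ORR is exposed only if a patient who would have responded has not been assessed at the cut. Results are reported by cohort, so one lost responder among 20 patients moves ORR by 1/20 = 5 percentage points.

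Aligning SAP 5.1 with the current protocol would not help, because it would remove the only stated floor. The SAP floor is also loose: 2 months from enrollment (about 8.7 weeks) can end before a first scan due 7 to 9 weeks after a first dose that itself follows enrollment.

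**Working it through.** **Inputs from the documents.** The two limbs and the earlier-of rule (Protocol 10.3); first scan at 8 ± 1 weeks (Table JTJN.2); minimum about 20 per cohort, so about 80 in all, and maximum about 180 (Protocol 5.2); "ORR of 25% and 15% are considered the threshold of activity for Cohorts 1 – 3 and 4, respectively" (Protocol 10.3.4).

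**Assumptions.** The documents give no accrual rate or response timing. The simulation uses uniform accrual over 18 months, with 70% of responses at week 8 and 30% at week 16.

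**1. The plan's own figures.** Protocol 10.1 gives the chance of a run without responders, (1 − p)^n. For 0 of 6 at 25%, 0.75^6 = 17.8%. For 0 of 10 at 15%, 0.85^10 = 19.7%. Both reproduce.

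**2. Date arithmetic.** The last responder enrolls at month 8 and responds at month 10, so limb 1 falls at 10 + 6 = month 16. The last patient enrolls at month 15, so her first scan is at about month 17. Limb 2 falls at 15 + 12 = month 27. Month 16 governs and precedes her first scan.

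**3. Closed form.** If the last responder responded at her first scan, the scan lag cancels. The cut then precedes the last patient's first scan when nobody enrolled in the final 6 months of accrual responds. Given an earlier responder, P = (1 − p)^(6 × monthly accrual):

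| Patients/month | ORR 5% | 10% | 15% | 25% |
|---|---|---|---|---|
| 1 | 74% | 53% | 38% | 17.8% |
| 2 | 54% | 28% | 14% | 3.2% |
| 4 | 29% | 8.0% | 2.0% | 0.1% |
| 6 | 16% | 2.3% | 0.3% | about 0 |

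**4. Simulation (10,000 trials per setting, 18-month accrual).** The hindsight cut is min(last response + 6 months, last enrollment + 12 months), with the last response taken over all responders. The real-time cut is the first date, from last enrollment on, at which 6 months have passed since the latest response seen so far, with the same cap. Pairs give the chance that the cut precedes week 9 / week 17 of the last patient.

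| N | ORR | Hindsight | Real time | At least 1 responder missed (real time) |
|---|---|---|---|---|
| 80 | 5% | 21% / 33% | 36% / 48% | 15% |
| 80 | 10% | 5% / 12% | 13% / 20% | 8% |
| 80 | 20% | 0.2% / 1% | 1% / 2% | 1% |
| 120 | 5% | 11% / 21% | 22% / 33% | 12% |
| 120 | 10% | 1% / 4% | 4% / 8% | 3% |
| 120 | 20% | 0% / 0.1% | 0.1% / 0.2% | 0.1% |
| 180 | 5% | 4% / 10% | 9% / 16% | 6% |
| 180 | 10% | 0.1% / 1% | 1% / 2% | 1% |
| 40 (one cohort) | 10% | 21% / 32% | 35% / 48% | 15% |
| 20 (one cohort) | 25% | 11% / 20% | 27% / 37% | 17% |

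Under hindsight the share of trials with a responder after the cut is 0.0% in every row, as it must be: nobody responds after the last responder. The hindsight columns therefore measure immaturity of DCR and PFS, not loss from ORR.

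**5. Sensitivity to accrual.** For 80 patients at ORR 5%, 10% and 20%, the real-time chance of missing a responder is 9%, 3% and 0.1% over 12 months, and 16%, 13% and 3% over 24 months. For 180 patients over 30 months it is 14% at ORR 5% and about 4–5% at 10%.

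**6. Effect of a floor.** For 80 patients at 4 per month and ORR 5%, allowing 7 to 28 days from enrollment to first dose, the real-time cut precedes the last patient's first scan in 42% of trials. With an illustrative floor of 20 weeks after last enrollment, this falls to 0.

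**The case against.** A reader might infer that the hindsight percentages (11–21% at ORR 5% with 80 to 120 patients) show how often the primary ORR is biased. They do not. On that reading every unscanned patient is a true non-responder and the numerator is complete. Only the real-time reading loses responders, on average 0.06 to 0.19 per whole trial at ORR 5–10% with 80 to 120 patients, in cohorts already well below the activity thresholds.

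A reader might also infer that the primary analysis could come before enrollment closes. That is strained. The last responder of a study still enrolling is not identifiable, and Protocol 10.3.4 treats looks in that period as interim analyses: "It is planned that enrollment can continue while interim analyses are conducted".

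The futility rules limit the low-response case. With the illustrative Beta(1,1) prior, Pr(ORR > 25%) is 0.192 at 3/20 and 0.367 at 4/20, so Cohorts 1–3 need at least 4/20 to continue. The chance of that is 1.6% at ORR 5% and 13% at 10%. Long accrual at a very low rate is therefore unlikely in those cohorts. Cohort 4's rule is looser: at ORR 10% the chance of closing at 20 patients is 39%. Closing all four cohorts at the first interim still leaves about 80 patients. Low response is also plausible for Cohort 3, since Protocol 3.2.2.3 reports 0 responders among 6 evaluable *BRCA*-mutated patients in the earlier study.

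Optional updated analyses 6–12 months later and Kaplan-Meier censoring soften the PFS problem, so short follow-up there costs precision rather than validity. Neither repairs DCR at the primary analysis. The FDA recommendation behind the timing is not in the documents, and nothing in them says that it excluded a floor.

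**Conclusion.** The gap is real on the current text of Protocol 10.3, but its reach is limited.

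- **DCR and PFS.** Both are exposed on either reading if data are cut at the trigger date. With 80 patients and an 18-month accrual, the hindsight cut precedes week 17 of the last patient in 33% of trials at ORR 5% and 12% at 10%.
- **ORR.** It is understated only on the real-time reading: about 12–15% of trials miss at least one responder at ORR 5%, 3–8% at 10%, and 1% or less at 20% (80 to 120 patients). If the trigger is applied per cohort, the figure is about 15–16% for 40 patients at ORR 10%.
- **Operability.** In hindsight no responder is missed, but the date may already have passed when it becomes known.
- **Where it does not matter.** With no responders the 1-year limb governs. Study-wide, the risk is negligible at ORR 20% or more under 18-month accrual. With about 180 patients it is about 1% at ORR 10%, though 6% remains at ORR 5%.

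All percentages rest on assumed accrual and response timing, and they rise with slower accrual. The documents do not support a claim that the primary ORR is generally biased. They do support adding a floor and defining the trigger.

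**What to change.** Replace the sentence in Protocol 10.3, and the timing text in SAP 5.1, with: *The primary analysis will be conducted when every enrolled patient has had two scheduled post-baseline tumor assessments (about 17 weeks from first dose), or has progressed, died or left the study, and about 6 months have passed since the latest first response known at that time; but no later than about 1 year after the last patient is enrolled.* State whether this applies study-wide or per cohort.

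One detail for DCR: SAP Table JTJN.6.1 equates two scan intervals with 4 months, and two assessments match that convention. Counted in calendar months, 4 months is about 17.4 weeks, while the second scan falls at 15–17 weeks. The SAP should say which count applies to stable disease. If it is the calendar count, the floor needs a third assessment.

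Cost: one sentence in each document. In low-response scenarios the analysis comes a few months later, within the existing 1-year limit. Both the 6-month and the 1-year elements are kept, but the sponsor should confirm the wording against the FDA recommendation cited in Appendix 7.

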10.3.1. Efficacy Analyses

Overall response rate (ORR) is defined as the number of patients who achieve a best overall response of complete response (CR) or partial response (PR) divided by the total number of enrolled patients per cohort. The ORR, with corresponding 95% exact CI, will be summarized for each cohort. The posterior estimates of ORR and posterior probability of ORR that is greater than the cutoff value will also be derived via a Bayesian model. See details in Section 10.3.4.

Disease control rate (DCR) is defined as the number of patients who achieve a best overall response of CR, PR or stable disease for ≥ 4 months divided by the total number of enrolled patients per cohort. The DCR, with corresponding 95% exact CI, will be summarized for each cohort.

CA-125 response is defined as $\geq 50\%$ reduction in CA-125 levels from a pretreatment sample. The response must be confirmed and maintained for ≥ 28 days according to GCIG criteria. Patients must have a pretreatment sample that is ≥ 2 times the upper limit of the reference range and obtained within 2 weeks before starting the treatment. The response rate based on CA-125 will be summarized for each cohort.

Progression-free survival (PFS) is defined as the time from the first dose until the first occurrence of documented disease progression per RECIST 1.1, or death from any cause in the absence of progressive disease. Patients known to be alive and without disease progression will be censored at the time of the last adequate tumor assessment (a detailed PFS event/censoring scheme is provided in SAP).

Duration of response (DoR) is defined as the time from the date measurement criteria for CR or PR (whichever is first recorded) are first met until the first date that disease is recurrent or objective progression is observed, per RECIST 1.1, or the date of death from any cause in the absence of objectively determined disease progression or recurrence. The DoR will be censored according to the same rules as PFS.

Overall survival (OS) is defined as the time from the first dose until death from any cause. If the patient is alive, lost to follow-up or withdrawn from study at the time of data analysis, OS data will be censored on the last date the patient is known to be alive.

For time-to-event variables, such as PFS, DoR and OS, the Kaplan-Meier method (Kaplan and Meier 1958) will be used to estimate the curves, median time and 95% CI for each cohort.

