To estimate secondary efficacy measures including DCR, DoR, CA-125 response, PFS, OS	
 DCR: proportion of patients who achieve a best overall response of CR, PR and SD (for at least 4 months) as determined per RECIST version 1.1. DoR: time from the date measurement criteria for CR or PR (whichever is first recorded) are first met until the first date of documented PD, per RECIST 1.1, or the date of death from any cause in the absence of documented PD. CA-125 response: at least a 50% reduction in CA-125 levels from a pretreatment sample that is at least twice the upper limit of the reference range and obtained within 2 weeks before starting the treatment, with confirmation after 4 weeks according to GCIG criteria. PFS: time from enrollment until the first radiographic documentation (as assessed by the investigator) of progression or death from any cause in the absence of documented PD OS: time from enrollment until death from any cause

Abbreviations: AEs = adverse events; CR = complete response; DCR = disease control rate; DoR = duration of response; ECG = electrocardiogram; GCIG = Gynecologic Cancer Intergroup; ORR = overall response rate; OS = overall survival; PD = progressive disease; PFS = progression-free survival; PK = pharmacokinetics; PR = partial response; RECIST = Response Evaluation Criteria In Solid Tumors version 1.1 (Eisenhauer et al. 2009); SAEs = serious adverse events; SD = stable disease.

Overall Design:

Study JTJN is a multicenter, nonrandomized, parallel cohort, Phase 2 study in patients with high-grade serous ovarian, primary peritoneal, or fallopian tube cancer.

Patients will be assigned to the following cohorts:

- Cohort 1: Platinum-resistant, *BRCA* negative, and received ≥ 3 lines of prior therapy
- Cohort 2: Platinum-resistant, *BRCA* negative, and received < 3 lines of prior therapy
- Cohort 3: Platinum-resistant, *BRCA* positive, there is no restriction on number of lines of prior therapy, but patients must have received prior poly (ADP-ribose) polymerase (PARP) inhibitor
- Cohort 4: Platinum-refractory, *BRCA* positive or negative, no restriction on number of lines of prior therapy

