3.3. Benefit/Risk Assessment

Given the high unmet need for additional therapies to treat platinum-resistant or –refractory HGSOC, the mechanistic rationale supporting a role for CHK1 inhibition to improve outcomes for patients with HGSOC, nonclinical model data (including HGSOC) on prexasertib monotherapy, prexasertib clinical safety profile, and preliminary efficacy observed in patients with HGSOC, the risk/benefit assessment supports evaluation of prexasertib monotherapy in the proposed patient population. More information on known and expected benefits, risks, serious adverse events (SAEs), and reasonably anticipated AEs of prexasertib are described in the IB.

4. Objectives and Endpoints

Table JTJN.5 shows the objectives and endpoints of the study.

Table JTJN.5. Objectives and Endpoints

Objectives	Endpoints
Primary	
To estimate the ORR for each cohort	
 • ORR: proportion of all enrolled patients who achieve a best overall response of PR+CR as determined per RECIST version 1.1.
Secondary	
To characterize the safety and toxicity profile of prexasertib	
 • The safety endpoints evaluated will include but are not limited to the following: AEs, SAEs, clinical laboratory tests, ECGs vital signs, and physical examinations
To characterize the PK of prexasertib	
 • Prexasertib concentrations in plasma
To estimate secondary efficacy measures including DCR, DoR, CA-125 response, PFS, OS	
 • DCR: proportion of patients who achieve a best overall response of CR, PR and SD (for at least 4 months) as determined per RECIST version 1.1. • DoR: time from the date measurement criteria for CR or PR (whichever is first recorded) are first met until the first date of documented PD, per RECIST 1.1 criteria, or the date of death from any cause in the absence of documented PD. • CA-125 response: at least a 50% reduction in CA-125 levels from a pretreatment sample that is at least twice the upper limit of the reference range and obtained within 2 weeks before starting the treatment, with confirmation after 4 weeks according to GCIG criteria. • PFS: time from enrollment until the first radiographic documentation (as assessed by the investigator) of progression or death from any cause in the absence of documented PD • OS: time from enrollment until death from any cause
Tertiary/Exploratory	

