### 5.9.1. Primary Efficacy Analyses

**Overall response rate (ORR)** is defined as the number of patients who achieve a best overall response of complete response (CR) or partial response (PR) divided by the total number of enrolled patients per cohort. The ORR, with corresponding 95% exact CI, will be summarized for each cohort. The posterior estimates of ORR and posterior probability of ORR that is greater than the cutoff value will also be derived via a Bayesian model.

- Cohort 1, 2 and 3: posterior Pr (ORR>25%)
- Cohort 4: posterior Pr (ORR>15%)

**Disease control rate (DCR)** is defined as the number of patients who achieve a best overall response of CR, PR or stable disease for  $\geq 4$  months divided by the total number of enrolled patients per cohort. The DCR, with corresponding 95% exact CI, will be summarized for each cohort.

**CA-125 response** is defined as  $\geq 50\%$  reduction in CA-125 levels from a pretreatment sample. The response must be confirmed and maintained for  $\geq 28$  days according to GCIG criteria. Patients must have a pretreatment sample that is  $\geq 2$  times the upper limit of the reference range and obtained within 2 weeks before starting the treatment. The response rate based on CA-125, with corresponding 95% exact CI, will be summarized for each cohort.

**Progression-free survival (PFS)** is defined as the time from the date of enrollment until the first occurrence of documented disease progression per RECIST 1.1, or death from any cause in the absence of progressive disease (PD). Progression-free survival curves, median PFS, and PFS rates at 3 months intervals up to 12 months with 95% CI for each cohort will be estimated using the Kaplan-Meier (KM) method (Kaplan and Meier 1958).

If a patient is not known to have progressed or died at the time of analysis, PFS time will be censored at the last known progression-free assessment. The detailed censoring rules are described in [Table JTJN.6.1](#).

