**Table JTJN.6.1. PFS events/Censoring Scheme**

Situationa	Event/Censor	Date of Event or Censor
Tumor progression or death	Event	Earliest date of PD or death
No tumor progression and no death	Censored	Date of last adequate radiological assessment or date of randomization (whichever is later) b
Unless		
No baseline radiological tumor assessment available	Censored	Date of enrollment
No adequate postbaseline radiological tumor assessment available and death reported after missing 2 scan intervals following randomization b,c	Censored	Date of enrollment
Tumor progression or death documented immediately after missing 2 or more scan intervals following last adequate radiological tumor assessment or enrollment (whichever is later) b,c	Censored	Date of last adequate radiological assessment or date of enrollment (whichever is later) b
New anticancer therapy started before tumor progression or death	Censored	Date of last adequate radiological assessment prior to the start of new anticancer therapy or date of enrollment(whichever is later) b

Abbreviations: CR = complete response; PD = progressive disease; PFS = progression-free survival; PR = partial response; SD = stable disease.

- a Symptomatic deterioration (that is, symptomatic progression that is not radiologically confirmed) will not be considered as tumor progression.
- b Adequate radiological tumor assessment refers to an assessment with one of the following responses: CR, PR, SD, or PD.
- c 2 scan intervals = 4 months.

**Duration of response (DoR)** is defined as the time from the date measurement criteria for CR or PR (whichever is first recorded) are first met until the first radiographic documentation of progression or death from any cause in the absence of PD. The analysis is for confirmed responders only. Median duration of response will be estimated using the KM method. The DoR will be censored according to the same rules as PFS.

**Overall survival (OS)** is defined as the time from the date of enrollment until death from any cause. If the patient is alive, lost to follow-up or withdrawn from study at the time of data analysis, OS data will be censored on the last date the patient is known to be alive. Overall survival curves, median overall survival, and survival rates at 6 months intervals up to 24 months with 95% CI for each cohort will be estimated using the KM method.

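### Protocol 10.3.1 starts PFS and OS at first dose, while the protocol's endpoint tables and the SAP start them at enrollment; enrolled patients who are never treated then have no time zero

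*Protocol*

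**What the plan says.** Protocol Section 10.3.1 states that PFS "is defined as the time from the first dose until the first occurrence of documented disease progression per RECIST 1.1" and that OS "is defined as the time from the first dose until death from any cause". For PFS censoring it refers the reader onward: "a detailed PFS event/censoring scheme is provided in SAP".

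Everywhere else the clock starts at enrollment:

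- Protocol synopsis: "OS: time from enrollment until death from any cause", with PFS on the same origin.
- Protocol Table JTJN.5: "PFS: time from enrollment until the first radiographic documentation (as assessed by the investigator) of progression or death", with OS on the same origin.
- SAP Table JTJN.4.1 repeats the enrollment definitions. SAP 5.1 sets the time-to-event baseline at enrollment and explains that as the date of cohort assignment.
- SAP 5.9.1: PFS "is defined as the time from the date of enrollment until the first occurrence of documented disease progression per RECIST 1.1" and OS "is defined as the time from the date of enrollment until death from any cause". The planned OS outputs include "survival rates at 6 months intervals up to 24 months".

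Three other provisions bear on the choice. Protocol 10.2 uses the ITT set, meaning everyone assigned to a cohort, for efficacy. Protocol 10.1 allows for patients who are assigned but not treated. Protocol 8.3 seeks survival status for patients lost to follow-up, including those never given prexasertib.

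On scans, protocol Tables JTJN.2 and JTJN.3 set an 8-weekly schedule (±1 week) up to 1 year and a 12-weekly one after that. Footnote c of SAP Table JTJN.6.1 equates two scan intervals with 4 months throughout.

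**The concern.** PFS and OS are named secondary endpoints, and one protocol gives each of them two start dates. For treated patients the result is a shift equal to the time from enrollment to first dose. For enrolled patients who are never treated, a first-dose origin does not exist. If 10.3.1 is followed, OS becomes a treated-only endpoint inside an analysis set defined as all enrolled, and the survival data that Section 8.3 goes after cannot be used.

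The same holds for part of PFS. In SAP Table JTJN.6.1, death is an event. A patient without an adequate post-baseline scan is censored at enrollment if death comes after two missed scan intervals. A never-dosed patient who dies sooner is normally a PFS event, and 10.3.1 would drop it.

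There is also a mechanical misfit. Section 10.3.1 relies on the SAP censoring table, some rows of which censor at the enrollment date. With a first-dose origin, that date lies on or before time zero.

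A smaller matter sits in the same table. Footnote c can censor a genuine late progression, for PFS and DoR, after only one missed scan.

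**Working it through.** **1. Time origin.** Set side by side, 10.3.1 is the only outlier among the protocol and SAP definitions listed above. The summary of amendment (b) lists no change to these definitions, so the conflict is in current text.

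**2. Shift for treated patients.** The lag L from enrollment to first dose is not stated. Two readings bound it:
- Protocol 7.2 assigns a cohort to patients who meet all criteria. Inclusion criterion [9] includes predose Cycle 1 Day 1 values, and Table JTJN.2 lets those labs be drawn up to 3 days before dosing. Literally, L is about 0-3 days.
- Criterion [13] places the biopsy after eligibility is determined and within 28 days before Cycle 1 Day 1. I take 28 days as an assumed outer bound.

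With PFS exponential from first dose, S(t) = 0.5^(t/median), a fixed lag, and 30.44 days per month, the 3-month rate is S(3) from first dose and S(3 − L) from enrollment. Medians are assumed.

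| Median | From first dose | From enrollment, L = 3 d | From enrollment, L = 28 d |
|---|---|---|---|
| 3 months | 50.0% | 51.2% (+1.2) | 61.8% (+11.8) |
| 4 months | 59.5% | 60.5% (+1.0) | 69.7% (+10.3) |
| 6 months | 70.7% | 71.5% (+0.8) | 78.6% (+7.9) |

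If PFS is instead exponential from enrollment and patients are event-free when dosed, the hazard is constant and the curve from first dose is the same: 0 points at any lag. At a 4-month median the 28-day range is therefore 0 to about 10 points.

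**3. Never-dosed patients and OS.** Their number is not stated; assume a share q of 5-10% (1-2 of 20). If they survive like treated patients, leaving them out changes nothing. If their median OS is 3 months and that of treated patients is M1 (all assumed), 12-month OS of all enrolled = (1 − q) × 0.5^(12/M1) + q × 0.5^(12/3).

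| M1 | Treated only | All enrolled, q = 5% | All enrolled, q = 10% |
|---|---|---|---|
| 9 months | 39.7% | 38.0% | 36.3% |
| 12 months | 50.0% | 47.8% | 45.6% |
| 18 months | 63.0% | 60.2% | 57.3% |

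Treated-only OS is higher by 1.7 to 5.7 points.

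**4. Never-dosed patients and PFS.** At the same assumed 3-month median, the share dying within 4 months is 1 − 0.5^(4/3) = 60%. Unless another censoring row applies first, such as new anticancer therapy or no baseline scan, these are PFS events.

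**5. Footnote c.** Under the 8-weekly schedule, 2 × 56 = 112 days, or 3.7 months, which rounds to the stated 4. Under the 12-weekly schedule, 2 × 84 = 168 days, or 154-182 with the ±1-week windows at each end. Across the switch, 56 + 84 = 140 days, or 126-154. Both exceed 4 months on any reading (112 days with 28-day months, 120-123 by calendar). One missed scan therefore leaves a gap that the footnote treats as two.

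Size was found by simulation: 200,000 patients per setting; exponential PFS with medians of 3, 4 and 6 months; scans every 56 days to day 336 and then every 84 days, with ±7-day windows; 5% or 10% of scans missed at random; progressions only; cutoff 12 months after last enrollment, the latest date in protocol 10.3. The footnote (gap over 121.75 days) was compared with counting two or more missed scans. It alone censors about 1-4 post-year-1 progressions per 180 patients with 12-month accrual and 1-6 with 24-month accrual. Median PFS moves by at most 0.2 days and the 12-month rate by at most 0.4 points.

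**The case against.** The strongest reply is that the SAP governs the analysis and is consistent, so programmers would use enrollment and nothing would be lost. That makes harm less likely but does not remove the conflict: the protocol contradicts itself without the SAP. Protocol 10.3 expects a change of method to be described and justified in the SAP, and the SAP presents enrollment as neither a change nor a correction. The SAP (April 2018) also predates amendment (b) (September 2018).

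Second, PFS and OS are descriptive Kaplan-Meier estimates per cohort. Around 59.5%, a simple binomial 95% half-width is about 22 points at n = 20 (1.96 × √(0.595 × 0.405/20)) and 9 at n = 120, against about 1 point for a 3-day lag. This stands.

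Third, the assumptions pull against each other. If assignment waits for predose Cycle 1 Day 1 values, a never-dosed share of 5-10% is hard to expect. This also stands, and the OS effect may be zero.

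A reader might infer that PFS is misstated by some 10 points. That needs both the 28-day bound and one particular model; the literal reading of the eligibility text gives 0-3 days. A reader might also infer that footnote c distorts censoring in year 1. Under 8-weekly scanning one missed scan gives 112 days (98-126 with windows), so 4 months is a fair rounding and no year-1 claim is made.

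**Conclusion.** Section 10.3.1 is wrong as written. It conflicts with every other definition of PFS and OS in the protocol and SAP, leaves never-treated patients in the efficacy set without a start date, and does not fit the SAP rows that censor at enrollment.

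The numerical effect is probably small. It is about 1 point on 3-month PFS for a 3-day lag, 0 to about 10 points at the assumed 28-day bound with a 4-month median, and 0 to about 6 points on 12-month OS with 5-10% never dosed. The lag, the never-dosed share and the medians are all assumptions.

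A reader might carry this over to the primary result. The documents do not support that: ORR has no time origin, and the futility rules use ORR alone. DoR starts at first response, so the start date does not touch it; it does inherit footnote c.

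The footnote is a minor secondary point, with negligible effect on median PFS and on the planned PFS rates up to 12 months. The word randomization in SAP Table JTJN.6.1 is a slip in a nonrandomized study. The point should be corrected before analysis so that the origin is not chosen with data in hand.

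**What to change.** 1. In protocol 10.3.1, start PFS and OS at the date of enrollment, meaning cohort assignment, as in SAP 5.1.
2. In SAP Table JTJN.6.1, change randomization to enrollment in both places.
3. In the same table, revise footnote c:
   - Keep 4 months while the 8-weekly schedule applies. For never-dosed patients count it from enrollment, since the first scan is scheduled from Cycle 1 Day 1 and they have no scan calendar.
   - Once the 12-weekly schedule applies, or the gap spans the switch, censor only if two or more consecutive scheduled scans were missed.
   - Re-anchor the schedule after any confirmatory scan, as protocol Table JTJN.2 does, and count a late scan as the scheduled scan it replaces.

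A check of the revised rule after year 1, counting from an on-schedule scan: a death at day 150 follows one missed scan (window closed at day 91) and is an event. A death at day 178 with no intervening scan follows two (windows closed at days 91 and 175) and is censored. A progression on a scan at day 177, two days late, counts as the second scheduled scan, so only one was missed and it is an event.

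The cost is wording in one protocol section and one SAP table. No new data are needed.
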